6.1.3 Definition of DLT

As a general rule, DLT includes the observation of any of the side effects listed below during the DLT evaluation period and will ultimately be determined upon deliberation between the sponsor and the principal investigator of the trial. Furthermore, the opinion of the Data and Safety Monitoring Committee can be sought as required (refer to attachment 1: trial protocol [supplement]).

• Hematotoxicity:

–Persistent grade 4 neutropenia lasting \geq 7 days;

-When a neutrophil count of <1000/mm³ and fever of $\ge 38.0^{\circ}$ C is observed for >2 days;

-Grader 4 thrombopenia or thrombopenia associated with a hemorrhage requiring platelet transfusion.

- Grade 3 thrombocytopenia with bleeding.

• Non-hematotoxicity:

 \geq Grade 3 non-hematotoxicities. However, any of the following non-hematotoxicities will be deemed DLT when it is judged by the principal investigator or subinvestigator that treatment cannot be continued even with supportive therapy.

- \Rightarrow 2Grade 3 diarrhea, nausea, vomiting, and loss of appetite for \geq 5 consecutive days;
- \Rightarrow 2Grade 3 electrolyte imbalance for 27 consecutive days;
- \Rightarrow \geq Grade 3 dermal toxicity for \geq 7 consecutive days;
- ♦ Grade 3 or more immune related adverse event that lasts more than 8 days even after steroid therapy is applied.

• General:

When 70% of the planned regorafenib dose cannot be administered, and/or when one dose of nivolumab cannot be administered because of toxicity during the DLT evaluation period

6.1.4 Target subjects for DLT evaluation

For each level, at least three subjects will be enrolled, and the presence or absence of DLT will be evaluated during the DLT evaluation period.

When it is determined that there is a subject who will not change levels, an additional subject will

be enrolled to evaluate the DLT determined in 6.1.3.

Furthermore, among the enrolled subjects, those who meet the following conditions will be excluded from DLT evaluation:

1) Subjects who are unable to receive regorafenib for ≥ 14 days in the first course for reasons other than toxicity.

2) Subjects for whom sufficient data cannot be obtained to determine the DLT evaluation because of missing mandatory tests, etc.

3) Cases in which adequate data for DLT evaluation judgment could not be obtained due to essential test defects

Furthermore, among the participants who withdraw from regorafenib and nivolumab during the first course for reasons other than adverse events or who withdraw from treatment for a long period because of toxicities other than DLT, the decision to subject such patients to a DLT evaluation will be determined upon deliberation between the trial coordinating committee and the participating institution.

6.1.5 Determining transition to the expansion cohort

After completion of the final DLT evaluation period of the subjects in the dose escalating cohort, the decision to move the subjects into the expansion cohort will be determined once it is decided, upon deliberation between the sponsor and the principal investigator, that there are no problems associated with moving on. Furthermore, the opinion of the Data and Safety Monitoring Committee can be sought as required (refer to attachment 1: trial protocol [supplement]).

6.2 Criteria for the commencement and termination of the treatment protocol6.2.1 Criteria for terminating the treatment protocol

The treatment protocol will be terminated when the participating subjects meet any of the following criteria:

- 1) When an exacerbation of the underlying disease is observed (including marked exacerbation on diagnostic imaging, and clinically marked exacerbation).
- 2) When the subject requests to terminate the treatment protocol.
- 3) When treatment protocol-related grade 4 non-hematotoxicity is observed.

(However temporary abnormalities in test values shall not apply).

- 4) When nivolumab and regorafenib cannot be resumed for >28 days.
- 5) When the conditions for the termination of the treatment protocol apply as stipulated in "7.3 Criteria for changing the treatment protocol."
- 6) If the subject becomes pregnant.
- 7) When follow-up is not possible.
- 8) Death during the treatment protocol.
- 9) When 54 doses of nivolumab have been completed.
- 10) Termination following a CR.

Following at least eight cycles of nivolumab (approximately 6 months), when a subject is deemed to exhibit CR on the basis of diagnostic imaging, and receives at least two cycles of nivolumab after the initial determination of CR, termination of nivolumab can be considered upon consultation with the trial coordinating committee. The decision to terminate or continue regorafenib administration after CR can be considered by the attending physician upon consultation with the trial coordinating committee, regardless of whether nivolumab is terminated or continued.

11) Other instances when the attending physician judges it necessary to terminate the trial (including when treatment with other anticancer drugs, surgery, or radiotherapy not stipulated in the protocol is needed for lesions that are subject to evaluation).

When, despite meeting the criteria for termination of the treatment protocol, there are clinical grounds that strongly suggest the efficacy of the treatment and there are reasons that justify the continuation of the protocol treatment, the decision shall be reconsidered with the trial coordinating committee on an individual basis according to the situation.

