6.3.2 Criteria for changing the nivolumab dosage

Adverse events (irrespective of severity) associated with nivolumab exposure might be of immunological etiology. Such adverse events can occur immediately following the commencement of treatment with the investigational drug or several months after completion of treatment. For toxicities and severe or life-threatening adverse events with a causal relationship with nivolumab, the withdrawal and termination of nivolumab will be carried out in accordance with Table 6.3.2. For the guidelines regarding supportive therapy, including the use of corticosteroids, refer to section 6.3.2.1, and the investigator brochure (appendix 3 Management Algorithms).

In accordance with the instructions given in this section, administration is withdrawn and administration resumed. Subjects whose resumption of Nivolumab and Regorafenib need to be delayed for more than 28 days from the scheduled start date will cease protocol treatment. However, administration of Regorafenib was discontinued, but when Nivolumab resumption is possible according to 6.3.2, protocol treatment can be restarted with Nivolumab alone.

| Toxicity | Grade | Timing of | treatment | Instance | requiring | nivolumab |
|------------------|------------|----------------|-----------|--------------------------------------|-------------------|---------------|
| | requiring | resumption | after | termination | | |
| | withdrawal | withdrawal | | | | |
| Diarrhea/colitis | 2–3 | Toxicity is re | turned to | Terminate nivolumab when the subject | | n the subject |
| | | below grade | 1 | does not reco | over from toxic | ity within 12 |
| | | | | weeks of the | e last dose, or v | vhen |
| | | | | corticostero | ids cannot be d | ecreased to |
| | | | | below 10 mg | g/day of predni | solone |

Table 6: Criteria for nivolumab withdrawal and termination

| | | | within 12 weeks. |
|-------------------|----------------|-------------------------------------|--|
| | 4 | Nivolumab termination | Nivolumab termination |
| Elevated AST, | 2 | Toxicity is returned to | Terminate nivolumab when the subject |
| ALT, and/or | | below grade 1 | does not recover from toxicity within 12 |
| bilirubin | | | weeks of the last dose. |
| | 3-4 | Nivolumab termination | Nivolumab termination. |
| | | (see exceptions below) ^a | |
| Type I diabetes | T1DM | When clinically and | Terminate nivolumab when the subject |

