| (T1DM: when | or 3–4 | metabolically stable | is not clinically and metabolically stable |
| newly | | | within 12 weeks of the last dose. |
| developed) or | | | |
| hyperglycemia | | | |
| Hypophystitis | 2–4 | Toxicity is returned to | Terminate nivolumab when the subject |
| | | below grade 1. | does not recover from toxicity within 12 |
| | | When endocrine | weeks of the last dose, or when |
| | | hormone replacement | corticosteroids cannot be decreased to |
| | | therapy has been | below 10 mg/day of prednisolone |
| | | initiated. | within 12 weeks. |
| Hyperthyroidism | 3 | Toxicity is returned to | Terminate nivolumab when the subject |
| | | below grade 1 | does not recover from toxicity within 12 |
| | | | weeks of the last dose, or when |
| | | | corticosteroids cannot be decreased to |
| | | | <10 mg/day of prednisolone within 12 |
| | | | weeks. |
| | 4 | Nivolumab termination | Nivolumab termination |
| Hypothyroidism | Not | When thyroid hormone | |
| | stipulated | replacement therapy | |
| | | has been initiated | |
| Infusion reaction | 2 ^b | Toxicity is returned to | Terminate nivolumab when toxicity |
| | | below grade 1 | develops despite appropriate |
| | | | pretreatment. |
| | 3-4 | Nivolumab termination | Nivolumab termination |
| Pneumonitis | 2 | Toxicity is returned to | Terminate nivolumab when the subject |
| | | below grade 1 | does not recover from toxicity within 12 |
| | | | weeks of the last dose, or when |

| | | | corticosteroids cannot be decreased to | |
|-------------------|-------------------------------------|--------------------------|---|--|
| | | | <10 mg/day of prednisolone within 12 | |
| | | | weeks. | |
| | 3-4 | Nivolumab termination | Nivolumab termination | |
| Renal | 2 | Toxicity is returned to | Terminate nivolumab when the subject | |
| impairment or | | below grade 1 | does not recover from toxicity within 12 | |
| nephritis | | | weeks of the last dose, or when | |
| | | | corticosteroids cannot be decreased to | |
| | | | <10 mg/day of prednisolone within 12 | |
| | | | weeks. | |
| | 3-4 | Nivolumab termination | Nivolumab termination | |
| All other | Intolerance | The decision to | Terminate nivolumab when the toxicity | |
| toxicities with a | or persistent withdraw and resume g | | persists after drug withdrawal and is not | |
| causal | 2 | nivolumab can be made | returned <grade 1="" 12="" from<="" td="" weeks="" within=""></grade> | |

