| relationship | | at the discretion of the | the last dose. | |
| | | attending physician | | |
| | 3 or severe | Toxicity is returned to | Terminate nivolumab when the subject | |
| | | below grade 1 | does not recover from toxicity within 12 | |
| | | | weeks of the last dose, or when | |
| | | | corticosteroids cannot be decreased to | |
| | | | <10 mg/day of prednisolone within 12 | |
| | | | weeks. | |
| | 4 | Nivolumab termination | Nivolumab termination | |

Note: In the event that severe or \geq grade 3 side effects recur or when life-threatening toxicity develops, administration of the investigational drug will be terminated.

a. In patients with liver metastasis and HCC, any treatment for grade 2 AST and/or and ALT elevation will be resumed, and nivolumab treatment will be terminated when AST and/or ALT levels continue to be 50% higher than at baseline for \geq 1 week.

b. If the subject recovers from symptoms within 1 h of dose suspension, the dose will be resumed at an infusion rate of 50% of the initial rate (e.g., 50 mL/h from 100 mL/h). If the subject does not recover from symptoms within 1 h of dose suspension, the dose will be withdrawn until the symptoms recover and pretreatment will be administered at the time of the next dose. Refer to 6.3.2.1 for details.

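### For related grade 4 hypophysitis, and for grade 4 hyperglycemia that is more than a passing test value, 6.2.1 item 3 and Table 6 give conflicting instructions on nivolumab

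*Combined protocol and SAP*

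**What the plan says.** Section 6.2.1 lists criteria, any one of which ends protocol treatment. Item 3 is "When treatment protocol-related grade 4 non-hematotoxicity is observed", followed by one exemption: "However temporary abnormalities in test values shall not apply". The closing paragraph of 6.2.1 covers a patient who meets a criterion although clinical grounds strongly suggest that treatment is working. In that case "the decision shall be reconsidered with the trial coordinating committee on an individual basis according to the situation".

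Section 6.3.2 makes its table binding for withdrawing and terminating nivolumab after related toxicity. The text calls it Table 6.3.2; the caption reads Table 6. Two rows matter here.

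- **Hypophysitis.** The row begins "Hypophystitis | 2–4 | Toxicity is returned to". Grades 2 to 4 are grouped as requiring withdrawal, and the resumption column refers to recovery and to the start of hormone replacement. The termination column turns on recovery, or on lowering the steroid dose, within 12 weeks. It does not turn on grade.
- **New type 1 diabetes or hyperglycemia.** The row begins "Type I diabetes | T1DM | When clinically and" and continues "T1DM: when | or 3–4 | metabolically stable". Nivolumab may resume once the patient is stable. Termination follows only if stability is not reached within 12 weeks of the last dose.

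The note under the table adds that "when life-threatening toxicity develops, administration of the investigational drug will be terminated".

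**The concern.** Item 3 and Table 6 are both written as mandatory, and they point in different directions for the same event. After a related grade 4 hypophysitis, item 3 ends protocol treatment, while the table row tells the investigator when nivolumab may restart. Nothing in 6.2.1 or in the table note names the row as an exception, so a site cannot tell whether the difference is intended.

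What is at stake is mainly patient safety: whether a patient is exposed to nivolumab again after a serious related event would depend on which page the investigator opened. There are smaller consequences for the data. Time on treatment and the list of discontinued patients (12.12.2) would reflect the choice of passage. Under 11.2.3, a patient who stops because of an adverse event and starts another therapy is censored for PFS at that start, so the choice can also reach PFS. One or two further institutions are planned for the expansion cohort, which makes differing local readings more likely.

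**Working it through.** The plan gives no figure on this point, so the check compares the passages.

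**1. How Table 6 treats grade 4, row by row**

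| Table 6 row | Instruction that applies at grade 4 |
|---|---|
| Diarrhea/colitis | Terminate |
| AST, ALT, bilirubin | Terminate (grades 3–4), subject to footnote a |
| Type 1 diabetes/hyperglycemia | Resumption possible (T1DM or grades 3–4) |
| Hypophysitis | Resumption possible (grades 2–4) |
| Hyperthyroidism | Terminate |
| Hypothyroidism | No grade stipulated |
| Infusion reaction | Terminate (grades 3–4) |
| Pneumonitis | Terminate (grades 3–4) |
| Renal impairment/nephritis | Terminate (grades 3–4) |
| All other related toxicities | Terminate |

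The table has ten rows. Removing hypothyroidism leaves 10 − 1 = 9 that address grade 4. Two of these allow resumption, and 9 − 2 = 7 terminate nivolumab.

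**2. Hypophysitis against item 3.** The event is non-hematological. For grades 3–4, section 6.3.2.1 prescribes intravenous and then oral corticosteroids, so the protocol handles it as a clinical condition and not as a passing laboratory value. The exemption in item 3 therefore does not remove it. If it is treatment-related and grade 4, item 3 requires termination and the row provides for restarting. This is a direct conflict.

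**3. Hyperglycemia and type 1 diabetes against item 3.** Blood glucose is a test value, so a transient grade 4 reading can fall under the exemption; item 3 and the row then agree. Section 6.3.2.1 also describes type 1 diabetes, ketoacidosis and metabolic acidosis under this heading, and these are more than a passing reading. The conflict is limited to related grade 4 events of that kind. The grade 3 part of the row, and type 1 diabetes below grade 4, do not contradict item 3.

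**4. The two rows against the table note.** The note speaks of life-threatening toxicity, not of grade 4. The protocol's own tables describe grade 4 as life-threatening for hypertension (Table 4) and infusion reaction (Table 7), but Table 5 defines grade 4 liver abnormalities by laboratory multiples alone. The documents do not define grade 4 for hypophysitis or hyperglycemia. This second conflict is therefore conditional: it arises where the particular event is life-threatening.

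**5. Does any passage set the order of precedence?**

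- Item 5 of 6.2.1 already brings in the termination conditions of the treatment-change section. It cites that section as 7.3, under the title that 6.3 carries. Item 3 therefore reads as a separate, additional criterion.
- Section 6.1 allows one drug to continue when termination criteria are met for the other, after committee deliberation. It does not provide for restarting nivolumab after a nivolumab-related grade 4 event.
- The reconsideration paragraph of 6.2.1 requires strong signs of efficacy and an individual committee decision. The two rows require neither.

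None of these settles which instruction governs.

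**The case against.** The best defence is that a specific table should prevail over a general list, and that the committee routes can deal with the rare case. As a drafting convention the first part is reasonable, but the protocol does not state it, and where the event is life-threatening the table's own note sides with item 3. The committee routes are real and would catch some cases. They operate as waivers, case by case, and leave the two written rules as they are.

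The limits on impact stand. The documents give no expected frequency for either event at grade 4. DLT has its own definition in 6.1.3, and no effect on the MTD or RD has been shown. An effect on the list of serious deviations is also not shown, because 14.2 requires a major deviation to be clinically inappropriate and to meet two or more further conditions.

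A reader might also infer three stronger things that the documents do not support.

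- *Item 3 covers every grade 4 non-hematological event.* It does not, because temporary test-value abnormalities are exempt. This removes part of the hyperglycemia case.
- *Table 6 lets nivolumab resume after a life-threatening event.* The documents do not equate grade 4 with life-threatening for these two toxicities. Where an event is life-threatening, the table note itself calls for termination.
- *An investigator who stops and one who resumes both comply.* Resuming after a non-exempt related grade 4 event follows the row but departs from item 3.

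**Conclusion.** The inconsistency is real and narrow. It is clear for related grade 4 hypophysitis. For the type 1 diabetes/hyperglycemia row it holds only for related grade 4 events beyond a temporary abnormal value, and the further conflict with the table note holds only where the event is life-threatening. In extent, it concerns two of the nine rows that address grade 4.

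The number of patients cannot be calculated from the documents. It is likely to be small in a trial planned at about 39 to 48 patients (9–18 plus about 30, section 2.8.2, before any added patients). The conclusion assumes that the event is judged related to protocol treatment and that the table rows are read as laid out above. It is worth correcting because it concerns a stopping instruction and costs little to repair. It is not evidence against the dose-finding design or the analysis.

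**What to change.** Reconcile 6.2.1 item 3, the hypophysitis row, the type 1 diabetes/hyperglycemia row and the Table 6 note so that they give one instruction for each event, and state which passage governs if they differ. Either item 3 and the note name these rows as exceptions, or the rows are brought into line with item 3 and the note. The clinical team decides which rule applies; this review takes no position. The text should also make clear when a grade 4 glucose value counts as temporary for the purpose of item 3.

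The cost is about one sentence or two table cells, processed under the protocol-change procedure in 13.4. No analysis, sample size or data collection changes.

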6.2.2 Data collection after treatment termination and the follow-up of subjects

When the criteria for termination are satisfied, the treatment protocol will be terminated. The time, reason, and progress associated with termination will be recorded on a case report form (CRF), and the prescribed tests will be conducted during the following observation period. However, when the attending physician judges that various tests cannot be performed or are not required for ethical reasons or for the safety or benefit of the subject, such tests shall not apply.

6.3 Criteria for changing the treatment protocol 6.3.1 Criteria for changing the dose of regorafenib

The safety profile of regorafenib has been established in the clinical trials noted above. The dose adjustments for regorafenib are according to the clinical trials conducted to date. Dose modifications are to be applied in 40 mg (one tablet) steps. When treatment with regorafenib is terminated because of any reason, the continuation of nivolumab monotherapy as the treatment protocol is permitted. The maximum daily dose is 160 mg.

| Table 0.3. I Day uuse of Regulateriib | | | |
|---------------------------------------|-------------------------|--|--|
| Level | The dose of Regorafenib | | |
| 0 | 40 mg/day(40 mg 1Tab) | | |
| 1 | 80 mg/day(40 mg 2Tab) | | |
| 2 | 120 mg/day(40 mg 3Tab) | | |
| 3 | 160 mg/day(40 mg 4Tab) | | |
| | | | |

Table 6.3.1 Day dose of Regorafenib

6.3.1.1 Dose adjustments for skin reactions of the hands and feet

When skin reactions of the hands and feet occur during regorafenib treatment, dose adjustments will be made at the discretion of the principal investigator(or subinvestigator) with reference to "Table 3: Dose adjustments for skins reactions of the hands and feet." Furthermore, in subjects who receive a dose reduction, when no \geq grade 2 rash or skin reaction of the hands and feet is observed at the decreased dose level throughout the subsequent cycle, the dose of the investigational drug can be increased to the starting dose at the discretion of the principal investigator (or subinvestigator).

Table 3: Dose adjustments for skins reactions of the hands and feet

Table Dose modification of hand-foot skin reaction

| NCI CTC Grade | | Dose adjustment | |
|---------------|---|--|--|
| | Painful erythema and swelling or discomfort of | Support supportive therapy as necessary. | |
| | hands and feet that interfere with daily living | Take asleep until toxicity relieves to | |
| Grade 2 | | Grade 0 to 1. When dosing is resumed, | |
| | | the same dose or dose is administered at | |
| | | a level reduced by 1 dose. | |
| Crada 2 | Wet scaling of limbs, work ulcers, blistering, | Wet scaling of limbs, work ulcers, | |
| Grade 5 | severe pain, or severe discomfort | blistering, severe pain, or severe | |

| | discomfort. |
|--|-------------|
| | |

6.3.1.2 Dose adjustment for hypertension

When hypertension develops during regorafenib treatment, dose adjustments will be made at the discretion of the principal investigator (or subinvestigator) with reference to "Table 4: Dose adjustments for hypertension." Hypertensive subjects require careful observation and it is strongly recommended to administer suitable hypotensive treatment during regorafenib treatment. The selection of hypotensive drug will be determined by the principal investigator (or subinvestigator) upon consideration of the treatment guidelines for each institution participating in the trial.

Furthermore, in subjects who receive a dose reduction, when hypertension is controlled for at least one cycle, the dose of the investigational drug can be increased to the starting dose at the discretion of the principal investigator (or subinvestigator).

| NCI-CTCAE grade | Dose adjustment |
|---|---|
| Grade 2 Systolic blood pressure of 140–159 mmHg and/or diastolic blood pressure of 90–99 mmHg, or when the former is normal but diastolic blood pressure is increased > 20 mmHg and accompanied by symptoms. | Continue the dosing. If poorly controlled, consider a dose reduction. When accompanied by symptoms, withdraw treatment until the subject recovers from the symptoms, and diastolic blood pressure is restored to <90 mmHg. When resuming treatment, continue at the same dose level. |
| Grade 3 Elevated systolic blood pressure of ≥160 mmHg and/or diastolic blood pressure of ≥100 mmHg, or pharmacotherapy of two or more types, and greater intensive therapy than before is needed. | Withdraw treatment until the diastolic blood pressure is decreased below 90 mmHg and if there are accompanying symptoms, until the subject recovers from the symptoms. When resuming treatment, consider decreasing the dose. When hypertension cannot be controlled with the addition of new hypotensive drugs or with more intensive therapy, decrease the dose by one level. When grade 3 hypertension recurs despite decreasing the dose and hypotensive treatment, |

Table 4: Dose adjustment for hypertension

| | decrease the dose further by one level. |
|---|---|
| Grade 4 | Terminate the administration of the |
| Life-threatening (e.g., malignant hypertension, | investigational drug. |
| temporary or constant neuropathy, and | |
| hypertensive crises). | |

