From cycle 2 onward, the treatment will commence after verifying that the dosing criteria listed in section 6.3 have been satisfied. The start day for nivolumab will be defined as day 1, including the washout period even in the event of conflict with the criteria defined in 6.3, and one cycle will last 28 days. If nivolumab is terminated and treatment is resumed as regorafenib monotherapy, the subsequent day of regorafenib resumption will be defined as day 1. In such an instance one cycle will also last 28 days.

Treatment will continue until the "criteria for treatment termination" are satisfied.

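### Table 4's grade 3 hypertension hold can start on systolic pressure alone but ends on diastolic pressure, so an asymptomatic patient at 175/85 qualifies for restart at the reading that starts the hold

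*Combined protocol and SAP*

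**What the plan says.** Section 6.3.1.2, Table 4, grade 3 row, has two blood pressure triggers: "Elevated systolic blood pressure of ≥160 mmHg and/or diastolic blood pressure of ≥100 mmHg". A third route into the row is a need for intensified drug treatment: "pharmacotherapy of two or more types, and greater intensive therapy than before is needed".

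The action is "Withdraw treatment until the diastolic blood pressure is decreased below 90 mmHg and if there are accompanying symptoms", until the patient has recovered from those too. On restart, a lower dose is to be considered. The row then says: "When hypertension cannot be controlled with the addition of new hypotensive drugs or with more intensive therapy, decrease the dose by one level". If grade 3 hypertension recurs despite this, a further one-level reduction follows.

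The paragraph above the table says that "dose adjustments will be made at the discretion of the principal investigator (or subinvestigator) with reference to" Table 4. For grade 2 hypertension without symptoms the table says "Continue the dosing. If poorly controlled, consider a dose reduction". Section 6.1.1 adds: "From cycle 2 onward, the treatment will commence after verifying that the dosing criteria listed in section 6.3 have been satisfied".

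**The concern.** The conditions for starting and ending the hold do not match. Systolic pressure alone can start it, but systolic pressure plays no part in ending it. A site could follow the release wording exactly and restart regorafenib in a patient whose systolic pressure still meets the row's own grade 3 definition. Sites that read the row by its purpose would wait longer. Different sites could then treat the same patient differently, and one or two further institutions are planned for the expansion cohort.

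Section 2.6.2 lists hypertension as the most frequent event of grade 3 or higher with regorafenib (15.6%). That figure covers all such hypertension. It does not measure the subset with raised systolic and normal diastolic pressure.

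**Working it through.** This is a check of logic; the plan has no figure to reproduce.

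**Inputs (Table 4, grade 3 row)**

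- Trigger: systolic ≥160, or diastolic ≥100, or intensified drug treatment needed.
- Current release: diastolic <90, and no symptoms or symptoms recovered.
- Proposed release: systolic <160 and diastolic <90, and no symptoms or symptoms recovered.

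**Readings in an asymptomatic patient**

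| Reading | Trigger met? | Current release met? | Proposed release met? |
|---|---|---|---|
| 175/85 | Yes (175 ≥160) | Yes (85 <90) | No |
| 160/89 | Yes (160 ≥160) | Yes (89 <90) | No |
| 150/102 | Yes (102 ≥100) | No | No |
| 150/85, drug treatment intensified | Yes (third route) | Yes | Yes |

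At 175/85 the systolic value is 175 − 160 = 15 mmHg above the trigger, and the diastolic value is 90 − 85 = 5 mmHg below the release value. Hold and release are met at one reading. The narrowest affected reading in whole mmHg is 160/89, a pulse pressure of 160 − 89 = 71 mmHg. The rule works for a hold triggered by diastolic pressure, as at 150/102. A hold started with both pressures raised can also end with systolic still at 160 or more, if the diastolic falls first.

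**Is a systolic release value given elsewhere?**

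- Section 6.1.1 sends the reader back to section 6.3 before each cycle from the second onward, and so to this row.
- The systolic limits in exclusion criterion 3 (≥160 in the summary, ≥150 in section 4.2) govern entry to the trial only.
- Table 6.3.1.4 holds regorafenib for grade 3 events until grade 2 or lower, but it covers other adverse events. Hypertension has its own table.
- The grade 2 row of Table 4 also uses diastolic <90 to end its hold for symptoms. Its systolic range stops at 159, where the same row continues dosing in patients without symptoms, so it does not permit a restart at grade 3 systolic pressure.

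**Comparison within the protocol.** Table 5 (section 6.3.1.3), grade 3, first occurrence, is triggered by bilirubin or by AST/ALT and gives a recovery value for each. Table 4 gives one for only one of its two blood pressure triggers.

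**The case against.** The strongest reply is that the row should be read as a whole. At 175/85 the grade 3 condition still holds, so the instruction to withhold still applies, and wording about a fall in diastolic pressure presupposes that it was raised. On that reading the row is ambiguous; it does not license a restart. Table 4 also operates under investigator discretion, which Table 5 does not state, so Table 5 is an imperfect comparator. Weekly blood pressure checks for the first 6 weeks (Table 8.2) would show a high systolic value soon after a restart. The diastolic-only release may also be inherited, since section 6.3.1 states: "The dose adjustments for regorafenib are according to the clinical trials conducted to date". Finally, the existing diastolic value clears the whole grade 2 band (90–99), so the parallel systolic value would be <140, not <160.

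Much of this stands as a limit on the consequence. Discretion makes a careless restart less likely, and uncontrolled or recurrent grade 3 hypertension leads to a lower dose. The documents cannot show whether the wording is inherited, and the choice between <160 and <140 is open. None of it supplies a systolic condition for ending the hold. The reduction steps set the dose, not the time of restart. Monitoring would detect a restart at high pressure but not prevent it. Discretion is exercised with reference to a table whose stated endpoint is the wrong one for this patient. Inheritance would explain the mismatch without removing it.

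**Conclusion.** The gap is real. One of the grade 3 row's two blood pressure triggers has no release value, and no other section supplies one. For asymptomatic readings with systolic ≥160 and diastolic <90, the release wording, followed exactly, allows regorafenib to resume at grade 3 systolic pressure.

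This rests on reading the trigger's and/or as allowing systolic pressure alone, and on taking the release clause at its word. How many patients are affected cannot be estimated from the documents. The point concerns patient safety and consistent handling between sites; it changes no sample size, error rate or planned analysis. It should be corrected because the existing rule can give an unsafe result when followed and the correction is small.

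**What to change.** In the grade 3 row of Table 4, replace the release condition with: withhold until systolic pressure is below 160 mmHg and diastolic pressure is below 90 mmHg, and until any symptoms have resolved.

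The value 160 is the row's own boundary. Below it, a patient without symptoms is in the range where the grade 2 row already continues dosing, or lower. The patient at 175/85 would stay on hold until systolic pressure had fallen by at least 175 − 159 = 16 mmHg. The sponsor may prefer a stricter value; with <140 the required fall would be at least 175 − 139 = 36 mmHg.

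The change does not resolve entry through drug intensification: such a patient at 150/85 meets the release under both wordings. If the sponsor wants a hold there, it needs its own condition.

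The cost is one clause. Both pressures are already recorded (Table 8.1), so no visit or measurement is added. The downside is a somewhat longer interruption of regorafenib for a few patients.
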